Study Comparing the Efficacy, Safety, and Cost of a Permanent, Synthetic Prosthetic Versus a Biologic Prosthetic in the One-stage Repair of Ventral Hernias in Clean and Contaminated Wounds.

NCT02041494

Document Date: July 23, 2014

STUDY PROTOCOL. The specific hypothesis driving the research application is that the use of a permanent synthetic prosthetic for the one-stage repair of complex ventral hernias will result in superior outcomes compared to a biologic prosthetic.

General study design. We propose a prospective, randomized, single-blind study in 330 patients with complex ventral hernias. A permanent synthetic prosthetic will be compared to a biologic prosthetic for clinical superiority. The primary endpoint is ventral hernia recurrence rate.

Eligible patients will be randomized to undergo open ventral hernia repair using either a permanent synthetic or a biologic prosthetic. Patients will be randomized while in the operating room using a technique of stratified randomization with permuted blocks to insure a balance between the two treatment groups at study entry. Patients assigned the synthetic code will be treated using the permanent synthetic prosthetic (Ventralight®, Bard, Murray Hill, NJ), whereas those patients assigned the biologic code will be treated with the biologic prosthetic (Strattice®, LifeCell Corp., Branchburg, N.J.). The selection of the synthetic and biologic prosthetics was based on a combination of established clinical experience and our best analysis of the available preclinical data. [33-39] Ventralight is a composite product that combines a synthetic mesh with a proven absorbable hydrogel barrier to minimize tissue attachment (adhesions) to the mesh. Strattice is a non-crosslinked, terminally sterilized, porcine dermal product recently introduced in 2007. While there is limited human data available, a multi-institutional trial evaluating its outcomes during the repair of infected and contaminated hernias was recently published. [6] Prior to the random assignment to receive either a permanent synthetic or a biologic prosthetic, patients will be stratified according to 3 factors;

- a) Charlson Index score, to ensure a balance of severity in chronic illnesses of the two patient groups;*
- b) Wound contamination, to ensure a balance between clean versus contaminated repairs in the two patient groups; and*

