- c) Surgical technique, to ensure a balance between hernia repairs where the prosthetic bridges the fascial defect versus reinforces a primary fascial closure*

Patients will be enrolled only once.

Patients will undergo daily evaluations during their index hospitalization. Follow-up will consist of evaluations by the investigator-surgeon before and at 1 month after surgery. The study team will perform follow-up evaluations at 3, 6, 12, 18, and 24 months after surgery or until the patient's hernia recurs. (Table 1) Due to the scheduling challenges involved, we will allow for a two-week window around the patients' targeted post-operative evaluation times. Patients will be followed for a total of 24 months since there is good evidence that the majority of hernia recurrences will take place within the first 18-24 months after surgery. [19, 20, 40, 41] Each evaluation will include a brief clinical examination, laboratory analyses, (complete cell count and differential, serum electrolytes, creatinine, urea nitrogen, albumin, prealbumin, C-reactive protein, Hgb A1c, liver function tests, urinalysis), anterior and lateral photographs of the abdomen, and ultrasound examinations of the anterior abdominal wall. During the scheduled visits wherein blood draws will occur, plasma will be banked for possible future research, considering the future potential of using antibodies as biomarkers. Evaluations of patient well-being, including a visual pain survey, Activities Assessment Score, and SF36 and HerQLes quality-of-life questionnaires (Appendices 1-4) will be performed at enrollment and 1, 6, 12 and 24 months following surgery. In addition, this panel of well-being assessments will also be administered when a patient develops a wound occurrence and/or hernia recurrence. An abdominal CT scan with intravenous contrast and volumetric analysis of the hernia will be obtained before surgery and 24 months after the hernia repair or when the patient's hernia recurs. The patient-related factors of gender, ethnicity, age, body-mass index (BMI, with obesity defined as a BMI \geq 30), chronic obstructive pulmonary disease, cough, constipation, prostatism, diabetes mellitus, glucocorticoid therapy, chronic immunosuppression, smoking status (current activity and pack-years), location of the hernia and abdominal surgery history (including prior ventral or inguinal hernia repairs) will be recorded. Perioperative factors including the patient's ASA score, size of the fascial defect (area in cm² = craniocaudal x transverse dimensions in cm), use of component separation repair techniques, duration of the operation, estimated blood loss, blood transfusion, maximum and minimum body temperature, maximum and minimum systolic blood pressure, vasopressor administration, perioperative antibiotics (including antibiotic regimen, timing of first dose and duration of therapy), postoperative complications, hospital length of stay, total hospital and professional charges and mortality will also be recorded.

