Study Comparing the Efficacy, Safety, and Cost of a Permanent, Synthetic Prosthetic Versus a Biologic Prosthetic in the One-stage Repair of Ventral Hernias in Clean and Contaminated Wounds.

NCT02041494

Document Date: July 23, 2014

STATISTICAL ANALYSIS PLAN

Data Analysis. The primary efficacy endpoint is the ventral hernia recurrence rate between the two treatment groups. Secondary endpoints will consist of comparisons of wound occurrences, perioperative complications, hospital length of stay, total hospital charges, pain, and quality of life. Continuous endpoints of hospital length of stay, total hospital charges, pain, and quality of life will be compared by the Mann-Whitney *U* test. The binary variables—wound infection, and perioperative complications—will be compared using Fisher's exact test. The cumulative percentages of patients with recurrences over time will be calculated and compared by using Kaplan-Meier curves and log-rank tests. We will investigate subgroup effects by comparing the size of the fascial defect (area in cm^2), patient co-morbidities, and clean versus contaminated wounds. All statistical tests will be two-sided. The primary analysis will be performed on an intention-to-treat basis for which patients will remain in their assigned group, even if during the procedure the surgeon judged the patient not to be suitable for the prosthetic or technique assigned. In addition a per-protocol analysis will also be performed for which patients with major protocol violations will be excluded.

Power Analysis: Overall, ventral hernia repairs recur with an estimated frequency of approximately 40%. However, conventional wisdom recognizes that wound contamination potentially doubles the risk of hernia recurrence. Therefore, we performed separate power analyses for hernia repairs under clean versus contaminated wound conditions that were informed by the medical literature and clinical studies we have conducted at UCSF.

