Clean wounds. Published data from our medical center noted an overall hernia recurrence rate of about 20% in predominantly clean wounds [43]. Similarly, our most recent retrospective analysis indicated hernia recurrence rates of 20%-30% and 50%-60% using synthetic versus biologic mesh, respectively, regardless of wound contamination (submitted for publication). Consequently, the power analysis for ventral hernia repairs under clean conditions indicates the need for 80 patients in each group, assuming a two-sided 0.05 level test and 80% power, and hernia recurrence rates of 40% versus 20% for patients receiving biologic versus synthetic prosthetics, respectively. The estimated recurrence rate of 40% with biologic mesh is consistent with estimates from the current medical literature [32].

Contaminated wounds. If we continue to assume a two-sided 0.05 level test and 80% power, and increase the estimated hernia recurrence rate from 40% to 60% for biologic prosthetics and from 20% to 30% for synthetic prosthetics used under contaminated conditions, then we will need to enroll a total of 40 patients in each group.

In total, we plan to enroll 250 patients to account for an anticipated drop out rate of <5% (**Table 2**). It is anticipated that approximately 40-45 patients will enroll in each of the study's next two (2) years. The nine active clinicians participating the trial perform approximately 175-200 open ventral hernia repairs per year. This enrollment target should guarantee that our study is adequately powered to demonstrate a significant difference in hernia recurrence rates, if present. Importantly, we have already demonstrated the ability to randomize ventral hernia repair patients to either treatment arm, a challenge that has effectively stymied other active studies (NCT02451176).

	Assumed recurrence rate for synthetic-mesh repairs	Assumed recurrence rate for biologic-mesh repairs	Required Sample Size for both groups (N_T)
Clean wounds	20%	40%	160
Contaminated wounds	30%	60%	80

Table 2. Power analysis.

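### Randomisation is stratified by three factors, but the SAP does not say whether the recurrence log-rank test is stratified or which test is primary; saying so is a small, cheap gain

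*SAP*

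**What the plan says.** Protocol, General study design: "Patients will be randomized while in the operating room using a technique of stratified randomization with permuted blocks". Before assignment, "patients will be stratified according to 3 factors": Charlson Index score, clean or contaminated wound, and technique. The third is given as "Surgical technique, to ensure a balance between hernia repairs where the prosthetic bridges the fascial defect" or reinforces a fascial closure. The Charlson cut-points are not stated in either document.

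SAP, Data Analysis: hernia recurrence is the primary efficacy endpoint, all tests are two-sided, and the only comparison named for recurrence is this: "The cumulative percentages of patients with recurrences over time will be calculated and compared by using Kaplan-Meier curves and log-rank tests". No strata, covariates or regression model are mentioned. Two of the randomisation factors reappear only in the list of subgroup comparisons: "patient co-morbidities, and clean versus contaminated wounds". Technique appears only in the intention-to-treat sentence, which keeps patients in their assigned group "even if during the procedure the surgeon judged the patient not to be suitable for the prosthetic or technique assigned".

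SAP, Power Analysis: clean and contaminated wounds are powered separately, on the stated ground that "conventional wisdom recognizes that wound contamination potentially doubles the risk of hernia recurrence". Table 2 uses 40% v 20% (biologic v synthetic) for clean wounds and 60% v 30% for contaminated wounds.

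**The concern.** Stratified randomisation removes chance imbalance on the stratification factors, so it reduces the true variance of the treatment comparison when those factors predict outcome. A test that ignores the factors still uses the larger, unstratified variance. It does not inflate type I error, but it rejects slightly too seldom and gives up some power. The SAP plans on contamination being prognostic: 1.5-fold in Table 2, and possibly 2-fold in the text.

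The silence leaves three further choices open:

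- **Pooling.** Power is given by wound class, and the SAP refers to log-rank tests in the plural without naming one overall test as primary.
- **Which stratum values apply.** The SAP foresees technique changing during the operation. The protocol (Surgical techniques) has wound class and technique recorded when the procedure ends, so those records may differ from the values used to randomise.
- **The interim.** The protocol (Study Stopping Rules) plans one efficacy look at 50% information but does not name the test statistic.

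**Working it through.** **1. The plan's own sample sizes.** With two-sided 0.05 and 80% power, n per group = (1.960 + 0.842)² × [p₁(1−p₁) + p₂(1−p₂)] / (p₁−p₂)².

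- Clean: 7.849 × (0.24 + 0.16) / 0.04 = 78.5, so 79 (SAP: 80).
- Contaminated: 7.849 × (0.24 + 0.21) / 0.09 = 39.2, so 40 (SAP: 40).

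The pooled-variance form gives 82 and 42. The total is 160 + 80 = 240, and 240 / 0.96 = 250. The SAP's figures reproduce.

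**2. Power of one overall test.** Assume the 2:1 clean:contaminated mix implied by 160 and 80.

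- Biologic: (2 × 40% + 60%) / 3 = 46.7%. Synthetic: (2 × 20% + 30%) / 3 = 23.3%.
- With 120 per arm, events are 56 + 28 = 84.
- Hazard ratio = ln(1 − 0.2333) / ln(1 − 0.4667) = 0.423.
- Log-rank power = Φ(0.861 × √84 / 2 − 1.96) = Φ(1.99) = 97.6%. The two-proportion formula gives 97.0%.

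Under Table 2 there is therefore little power left to gain.

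**3. Size of the conservatism, by hand.** Treat recurrence as binary, with no mesh effect and the same 2:1 mix.

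- *Contamination 1.5-fold (40%, 60%).* Overall rate 0.467, total variance 0.2489. Within-class variance (2/3)(0.24) + (1/3)(0.24) = 0.2400. Ratio 0.964, square root 0.982. Since 1.96 / 0.982 = 1.996, two-sided error is about 4.6%.
- *Contamination 2-fold (40%, 80%).* Overall rate 0.533, total variance 0.2489. Within-class variance (2/3)(0.24) + (1/3)(0.16) = 0.2133. Ratio 0.857, square root 0.926. Since 1.96 / 0.926 = 2.117, two-sided error is about 3.4%.

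**4. Simulation of the log-rank test.** There were 20,000 trials per setting, with recurrence detected at 3, 6, 12, 18 and 24 months. Assumed, because the documents do not give them: blocks of 4; one third contaminated; technique split 50/50; three Charlson levels at 50/30/20, so 12 strata; technique and Charlson not prognostic. Rejection rates in %, 240 patients:

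| 24-month rates: clean; contaminated | Unstratified | Contamination | Contamination + technique | All 12 strata |
|---|---|---|---|---|
| Table 2: 40 v 20; 60 v 30 | 97.5 | 97.8 | 97.8 | 97.6 |
| Smaller effect: 40 v 30; 60 v 45 | 46.9 | 48.5 | 48.3 | 47.6 |
| Hypothetical: 40 v 30; 80 v 60 | 57.7 | 66.8 | 66.6 | 65.2 |
| Null, 1.5-fold: 40/40; 60/60 | 4.7 | 5.0 | 5.0 | 5.1 |
| Null, 2-fold: 40/40; 80/80 | 3.4 | 4.9 | 4.9 | 5.0 |

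The null rows agree with step 3. In the smaller effect, 30% is the upper synthetic figure in the SAP's sentence "our most recent retrospective analysis indicated hernia recurrence rates of 20%-30% and 50%-60% using synthetic versus biologic mesh", and 40% and 60% come from Table 2. The 45% is assumed, and 80% v 60% appears nowhere in the documents.

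If technique is also prognostic (assumed hazard ratio 1.5 to 2.7), contamination + technique gives 48.6% to 52.7% in the smaller-effect case, against 46.1% to 46.6% unstratified.

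The protocol states 330 patients. At 317 evaluable (330 less an assumed 4%) the picture is the same: 99.4% v 99.4% under Table 2, and 56.7% v 58.4% for the smaller effect (unstratified v contamination + technique).

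**5. Where stratifying can lose power.**

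- *Contamination and the other factors not prognostic, 240 patients.* All 12 strata lose 0.5 point (40% v 25% in both classes) to 1.0 point (55% v 40%). A separate run gave 66.1% unstratified v 65.1%. Contamination + technique loses about 0.2 point or less.
- *120 patients (half of 240), Table 2 rates, tested at 1.96 and not at the interim boundary.* All 12 strata give 77.4% against 78.2% unstratified. Contamination alone gains about 0.8 point.
- *Five assumed Charlson levels (20 strata), smaller effect.* 46.0% unstratified, 45.9% with all strata, 47.5% with contamination alone.

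**6. Interim.** With the planned O'Brien-Fleming-type spending and one interim look (boundaries 2.963, then 1.969) and the same statistic at both looks, power stays within 0.3 point of the fixed test.

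**The case against.** The strongest reply is that nothing here is wrong. An unstratified log-rank is valid, the sample sizes reproduce, and under the plan's own rates the gain is about 0.3 point. That stands, and it is why the point is minor.

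The SAP also never says that its test is overall or unstratified. If the log-rank tests were run within wound class, contamination would already be handled. That stands too: the supportable point is that the test is under-specified, not that a poor one was chosen.

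Contamination may not be prognostic. The SAP attributes the doubling to conventional wisdom, and describes its retrospective rates as applying whatever the wound contamination. This stands as a limit. With contamination + technique the cost of being wrong is about 0.2 point or less, and Table 2 itself plans on a 1.5-fold effect.

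A reader might infer that the full three-factor stratified test is free and never worse. Step 5 shows otherwise: many small strata can lose up to about 1 point, and the Charlson categories are undefined. A reader might also infer from the 9-point case that the trial gives up some 50 patients' worth of information. That case needs contaminated rates of 80% v 60%, which the documents do not give. The retrospective biologic rates of 50%-60% quoted in the SAP point to a larger mesh effect, for which the gain would be small.

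**Conclusion.** The point holds as a minor, cheap improvement. The SAP does not say whether the recurrence test is stratified or that one overall test is primary, although randomisation is stratified by three factors. An overall unstratified test would be valid and mildly conservative: about 4.7% v 5.0% at the Table 2 contamination effect, and about 3.4% v 5% if contamination doubles risk.

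The power gain from stratifying is about 0.3 point under Table 2 and about 1.5 points for the assumed smaller effect. It reaches about 9 points only in the hypothetical case. The required sample size does not change.

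These figures rest on the 2:1 mix, blocks of 4 and the assumed technique and Charlson distributions. That the log-rank is the primary test is inferred from its being the only recurrence comparison named. The documents do not support reading this as an invalid test or as inflated type I error. The 330 v 250 enrolment figures are a separate matter, and the conclusion does not depend on which applies.

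**What to change.** Add to the SAP, Data Analysis:

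> The primary test is one overall two-sided log-rank test of hernia recurrence, stratified by wound contamination and surgical technique, using the values entered at randomisation. The same statistic is used at the interim and final analyses.

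If Charlson is to be included, state the categories used at randomisation. Add a rule, applied with arms pooled and before unblinding, that collapses Charlson to two levels or drops it when strata are sparse. The sparseness threshold should be written down in advance; fewer than 5 patients per stratum is one option, but its effect was not tested here. Contamination and technique stay in. The comparison by wound class remains a subgroup analysis.

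The cost is SAP wording only. The factors are already collected in order to randomise, so no patients, visits or data are added. The statistical price is about 0.2 point of power or less if neither retained factor is prognostic.

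### The SAP reports the percentage of patients with recurrence by Kaplan-Meier without a rule for death before recurrence; if deaths are censored, that percentage is slightly overstated

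*SAP*

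**What the plan says.** The SAP, under Data Analysis, defines the endpoint in one sentence: "The primary efficacy endpoint is the ventral hernia recurrence rate between the two treatment groups". The method follows later in the same paragraph: "The cumulative percentages of patients with recurrences over time will be calculated", with Kaplan-Meier curves and log-rank tests named for the calculation and the comparison. No other method is given for recurrence. Neither document says how a death before recurrence enters this analysis, calls death a competing event, or mentions a cumulative incidence estimator.

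The Protocol, under General study design, follows each patient for 24 months or until the hernia recurs. It closes a list of perioperative factors with "total hospital and professional charges and mortality will also be recorded". Death also appears in the Study Stopping Rules as an event that puts the trial on hold. Neither place gives an expected mortality rate or connects death to the recurrence analysis. The only loss figure is the SAP's anticipated dropout of under 5%, and it is not stated whether that includes deaths.

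**The concern.** The SAP sets out to report a percentage of patients. A patient who dies without recurrence can never join the numerator but belongs in the denominator. If Kaplan-Meier censors that patient at death, it implicitly assigns the later recurrence risk of the survivors. One minus Kaplan-Meier then describes a population in which nobody dies, and it exceeds the share who recur whenever recurrences occur after a death. The direction follows from the estimator and needs no outside evidence.

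What is at stake is the accuracy of the reported recurrence percentages, by arm and wound class, and of their difference. The log-rank test is not at stake. With deaths censored it still compares recurrence hazards among patients who are alive, given the usual independence assumption for other losses.

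**Working it through.** **Inputs from the SAP, Power Analysis.** For clean wounds the plan assumes "hernia recurrence rates of 40% versus 20% for patients receiving biologic versus synthetic prosthetics", and for contaminated wounds 60% versus 30%. Both calculations use a two-sided 0.05 test and 80% power. The results are 80 per group (clean) and 40 per group (contaminated).

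**Assumed, because the documents give no figure.** 24-month mortality m of 2%, 5% or 10%, equal in both arms; constant, independent hazards of recurrence and death.

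**Step 1: the plan's own figures.** With the unpooled two-proportion formula, n = (1.960 + 0.842)² × [p1(1-p1) + p2(1-p2)] / (p1-p2)².
- Clean: 7.849 × (0.24 + 0.16) / 0.04 = 78.5, so 79.
- Contaminated: 7.849 × (0.24 + 0.21) / 0.09 = 39.2, so 40.

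The pooled version gives 82 and 42. The stated 80 and 40 are reproduced to within 2 patients.

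**Step 2: what each estimator targets.** Let p be the 24-month risk that one minus Kaplan-Meier estimates with deaths censored, h = -ln(1-p) and g = -ln(1-m). The share of patients who actually recur is

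CIF = h/(h+g) × [1 - (1-p)(1-m)].

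Example, clean wounds, biologic arm, m = 5%: h = 0.5108, g = 0.0513, so CIF = 0.5108/0.5621 × (1 - 0.60 × 0.95) = 0.9088 × 0.43 = 0.3908. The excess is 40.00 - 39.08 = 0.92 points.

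**Step 3: all cells.** Entries are the CIF in percent, with the excess of one minus Kaplan-Meier in points in parentheses.

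| Assumed mortality | Clean, biologic (40%) | Clean, synthetic (20%) | Contaminated, biologic (60%) | Contaminated, synthetic (30%) |
|---|---|---|---|---|
| 2% | 39.63 (0.37) | 19.81 (0.19) | 59.49 (0.51) | 29.72 (0.28) |
| 5% | 39.08 (0.92) | 19.51 (0.49) | 58.71 (1.29) | 29.29 (0.71) |
| 10% | 38.13 (1.87) | 19.02 (0.98) | 57.40 (2.60) | 28.56 (1.44) |

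Simulation with 2 million patients per cell agrees. The clean-wound difference of 20.0 points becomes 19.8, 19.6 and 19.1 on the CIF scale; the contaminated difference of 30.0 becomes 29.8, 29.4 and 28.8. The overstatement of the difference is therefore about 0.2, 0.4-0.6 and 0.9-1.2 points.

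**Step 4: sensitivity to timing, m = 5%.** If recurrence is found only at the scheduled visits (months 1, 3, 6, 12, 18, 24), the excess per arm is 0.6 to 1.6 points rather than 0.5 to 1.3. If every death preceded every recurrence, the excess would be p × m, or 1.0 to 3.0 points.

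**Step 5: sensitivity to unequal mortality.** With equal mortality the excess in points is about 1.8 to 1.9 times larger in the biologic arm (at 5%: 0.92/0.49 and 1.29/0.71). With 2% biologic and 4% synthetic mortality the order reverses: 0.37 v 0.39 in clean wounds, 0.51 v 0.57 in contaminated wounds. The break-even ratio of synthetic to biologic mortality is about 1.9 (clean) and 1.8 (contaminated).

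**Step 6: scale.** At 5% mortality the largest excess is 0.92% of 80 = 0.7 patients in a clean-wound arm and 1.29% of 40 = 0.5 patients in a contaminated-wound arm. The 95% half-width for the difference is 1.96 × √(0.24/80 + 0.16/80) = 13.9 points (clean) and 1.96 × √(0.24/40 + 0.21/40) = 20.8 points (contaminated).

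**The case against.** The strongest reply is that this is partly a choice of target. Recurrence risk with deaths censored is a recognised way to compare how well repairs hold, and the SAP itself pairs its percentage with Kaplan-Meier. That is fair, but the sentence promises a percentage of patients, and a reader will take it as the share who recurred. If the other quantity is meant, the SAP should say so.

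The second reply is that the effect is immaterial at this sample size. On the figures above that is largely right, and it is why the point ranks as a refinement.

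A reader might also infer four stronger things that the documents do not support:
- **That the SAP censors deaths.** It does not say so. Censoring is the usual default; the documented gap is the missing rule.
- **That deaths are expected at some material rate.** Mortality is listed among perioperative factors, and Charlson stratification is there to balance chronic illness. A rule that holds the trial on a death suits a trial that expects few: at 10% mortality, about 25 of the SAP's 250 patients would die. If the under-5% dropout includes deaths, 10% also contradicts the plan.
- **That the bias is always larger in the arm with more recurrence.** This holds only in absolute points and with similar mortality in the arms. In relative terms the excess is slightly smaller there (at 5% mortality, 2.36% v 2.49% in clean and 2.19% v 2.43% in contaminated wounds). With enough extra synthetic-arm mortality, the difference between arms would be understated.
- **That the cost and quality-of-life results inherit the bias.** The SAP compares hospital charges, pain and quality of life separately by the Mann-Whitney test, and describes no analysis that feeds recurrence percentages into them.

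**Conclusion.** The point holds as a minor one. The SAP gives no rule for death before recurrence, and the default reading of its method does not estimate the percentage it promises. The upward direction in each arm is certain once deaths are censored and recurrences follow them. The size is not known: it rests on assumed mortality, constant hazards and, for the comparison of arms, equal mortality. On those assumptions it is at most 1.3 points per arm and 0.6 points on the difference at 5% mortality, and at most 2.6 and 1.2 points at 10%. Early deaths would raise the per-arm figure, to at most 3.0 points at 5%.

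No change to the sample size follows. The log-rank comparison is unaffected, and even if the trial compared actual proportions, the pooled formula at 5% mortality would give 84 and 44 per group instead of 82 and 42.

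**What to change.** Add a short statement to the SAP, Data Analysis:
- Death without recurrence is a competing event for recurrence.
- 24-month recurrence is reported by arm and by wound class (clean, contaminated) with the Aalen-Johansen cumulative incidence estimator and 95% confidence intervals.
- The cumulative incidence of death without recurrence is shown beside it, by arm, so that any imbalance in mortality is visible.
- The log-rank test is kept, described as a comparison of recurrence hazards, with deaths censored for that test.

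The cost is a sentence or two and standard software. The analysis needs only the dates of recurrence and death. Because the Protocol lists mortality with the perioperative factors, the sponsor should confirm that date of death is captured through month 24.

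### The primary recurrence comparison is an unadjusted log-rank test although four unstratified baseline variables are already collected: a missed efficiency of uncertain size, not an error

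*SAP*

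**What the plan says.** SAP, Data Analysis: "The primary efficacy endpoint is the ventral hernia recurrence rate between the two treatment groups". For that endpoint only one method is named: cumulative recurrence is to be "compared by using Kaplan-Meier curves and log-rank tests". No covariate is listed, and the SAP does not say that the test is stratified by the randomisation factors. Baseline characteristics appear only in the subgroup sentence: "We will investigate subgroup effects by comparing the size of the fascial defect", followed by co-morbidities and wound class.

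Protocol, General study design: randomisation takes place in the operating room and is stratified by Charlson score, wound contamination and surgical technique. On baseline data it says "An abdominal CT scan with intravenous contrast and volumetric analysis of the hernia will be obtained before surgery". BMI and smoking status with pack-years are listed as patient-related factors, and "abdominal surgery history (including prior ventral or inguinal hernia repairs) will be recorded". None of these four is a stratum. Table 1 places the CT and the history and examination at screening. Fascial defect area is listed separately, among the perioperative factors.

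**The concern.** A log-rank test has no term for a baseline predictor. Looking at subgroups asks whether the treatment effect varies; it does not sharpen the main comparison. If CT hernia size, BMI, smoking and earlier repairs predict recurrence, an analysis that uses them has more power from the same patients and corrects for chance imbalance in them. Naming them in advance also settles which covariates may be used, so that the choice cannot be disputed once results are known.

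The SAP sizes clean and contaminated wounds separately at 80% power, so neither class has a margin. The data are collected anyway. The question is how much is at stake.

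**Working it through.** **1. The plan's own figures.** Two-sided 0.05, 80% power, 1:1. With unpooled variance, n per group = (1.960 + 0.842)² × [p₁(1−p₁) + p₂(1−p₂)] / (p₁−p₂)².

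- Clean, 40% v 20%: 7.849 × (0.24 + 0.16) / 0.04 = 78.5, so 79. The SAP says its calculation "indicates the need for 80 patients in each group". The pooled-variance formula gives 82.
- Contaminated, 60% v 30%: 7.849 × (0.24 + 0.21) / 0.09 = 39.2, so 40, as stated. The pooled-variance formula gives 42.

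Both sizes reproduce. For the log-rank test with exponential times, HR = ln(1−0.2)/ln(1−0.4) = 0.437 and ln(1−0.3)/ln(1−0.6) = 0.389. The Schoenfeld formula then needs 46 and 36 events. The expected numbers are 160 × 0.30 = 48 and 80 × 0.45 = 36. The unadjusted test therefore delivers the planned power.

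**2. Both wound classes combined.** Biologic: (160 × 0.4 + 80 × 0.6)/240 = 46.7%. Synthetic: (160 × 0.2 + 80 × 0.3)/240 = 23.3%. With 120 per arm, power is 97.0%.

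**3. Effect of adjustment (simulation).** Recurrence times are exponential, with hazard multiplied by exp(s(Z₁+Z₂+Z₃+Z₄)/2), where the Zs are independent standard normal covariates, so s is the SD of the joint log-hazard score. Baseline hazards are calibrated so that the marginal 24-month risks equal the SAP's rates. Dropout is 5% and follow-up stops at 24 months. The unadjusted log-rank test is compared with the Wald test from a Cox model with the four covariates. There are 4,000 runs (2,000 for the combined case), with simulation error of about 0.6 points (0.4 combined). The documents give no value for s, so the range is an assumption.

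Power in %, log-rank → adjusted Cox:

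| s (AUC) | Clean, 80/arm | Contaminated, 40/arm | Combined, 120/arm |
|---|---|---|---|
| 0 (0.50) | 79.9 → 78.8 | 79.3 → 76.3 | 96.7 → 96.3 |
| 0.3 (0.60) | 80.2 → 80.2 | 79.7 → 79.1 | 96.9 → 97.1 |
| 0.5 (0.66) | 80.0 → 82.3 | 78.9 → 82.4 | 96.7 → 98.0 |
| 0.7 (0.71) | 80.3 → 84.6 | 79.5 → 86.7 | 96.9 → 98.7 |
| 1.0 (0.78) | 80.6 → 90.5 | 79.9 → 92.7 | 97.7 → 99.7 |

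**4. With stratification terms in the model.** Adding two binary strata, assumed non-prognostic (3,000 runs, error about 0.7 points), at s = 0.4, 0.6 and 0.8 gives 78.0 → 79.7, 80.0 → 82.8 and 78.1 → 85.8 in clean wounds. In contaminated wounds it gives 79.0 → 80.8, 79.7 → 82.8 and 80.5 → 87.2.

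**5. Type I error.** In the four-covariate model it was 4.6–5.4% for the log-rank test and 5.0–5.9% for adjusted Cox, highest at 40 per arm. With the strata added, at 40 per arm, it was 5.6% for the log-rank test and 6.2–6.5% for adjusted Cox.

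**6. Accrual shortfall.** The SAP expects 40–45 patients in each of the next two years, that is 80–90, and does not say how many are already enrolled. If the combined total were only 120 (an assumption), power would be about 77% unadjusted against 80, 84 and 90% adjusted at s = 0.5, 0.7 and 1.0. At 90 it would be 65–67% against 67, 72 and 79%.

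The simulations do not model detection at scheduled visits or the interim analysis.

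**The case against.** A reader might infer that the primary analysis throws away power for nothing in return, or that the log-rank test is the wrong test. The documents support neither.

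- The log-rank test is valid under randomisation, its error rate already allows for chance imbalance, and the stated sizes reproduce without adjustment. This stands.
- The SAP defines the primary endpoint between the two treatment groups and lists wound class under subgroup effects. Read that way, the primary comparison combines the classes and has little to gain at the planned size. This stands, except that the SAP's power section sizes each class separately, so the class-level figures remain relevant.
- Neither document says how strongly any of the four variables predicts recurrence. With weak predictors (s of 0.3 or below) there is no material gain, and uninformative ones cost power. This stands and makes the claim conditional.
- Adjustment has other costs. About 36 events are expected in contaminated wounds, so a long covariate list is unsafe there, and the Wald test runs slightly above its nominal level. This also stands.
- A reader might also infer that stratifying by the randomisation factors recovers nothing from the four variables. That goes too far. The Protocol's surgical technique section reserves reinforcement for fascial edges that can be brought together in the midline, which plausibly depends on defect size. The technique stratum may therefore carry part of that information; the documents do not say how much.

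What survives is narrower: variables recorded for every patient go unused in the main comparison, and using them requires only a decision in advance.

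**Conclusion.** The point holds as a recommended improvement. The SAP's sole named recurrence comparison ignores four unstratified baseline variables that the Protocol already collects.

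Over the assumed range of s from 0 to 1.0, adjustment changes power by about −1 to +10 points in clean wounds and −3 to +13 points in contaminated wounds. At moderate strength (0.5 to 0.7) the gain is about 2 to 5 and 3 to 7 points, and nearer the lower end once stratification terms are in the model. For the classes combined at about 240 patients it is at most about 2 points.

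The benefit therefore lies mainly in the wound-class comparisons sized at 80%, in protection if accrual falls short, and in correcting chance imbalance under a rule fixed in advance. These figures rest on the SAP's recurrence rates, exponential times, 5% dropout and an assumed prognostic strength.

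**What to change.** Before unblinding, amend the SAP's Data Analysis section to name as the primary recurrence analysis a covariate-adjusted log-rank (score) test, or a Cox model. It should be stratified by or adjusted for the randomisation factors, with a short list of covariates in stated forms:

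- one defined hernia size measure from the preoperative CT. The Protocol refers to volumetry and the SAP's subgroup sentence to defect area, so the measure must be named. Measurements taken during the operation should not be used;
- BMI, continuous;
- any earlier ventral hernia repair, yes or no, because the Protocol does not expressly require a count;
- current smoking.

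Within the contaminated class, use a reduced list or the score test. Report a standardised 24-month risk difference and keep the unadjusted log-rank test as a sensitivity analysis.

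The cost is SAP wording, with no new data. The downsides are a small loss of power if the covariates prove weak, a hazard ratio conditional on covariates if Cox is used (the standardised risk difference or the score test avoids this), and slight type I error inflation of the Wald test at 40 per arm. The simulations above used the Wald test, so the sponsor should check the chosen test by simulation at 40 per arm before fixing it.

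The planned total should be reconciled at the same time: the Protocol gives 330 patients and the SAP 250.
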